**F. Covariates and their corresponding assessment windows**

Table 3 provides an overview of the covariates and their corresponding assessment windows considered for inclusion in the PS model. These variables were selected *a priori* based on prior literature, including published studies [Izurieta 2020] and [Yih 2020], and discussions with clinicians, and conditions listed in the ‘COVID-19 associated hospitalization related to underlying medical conditions’ of the National Strategy for the COVID-19 Response and Pandemic Preparedness [Biden 2021, p.105]. Although all covariates will be considered, not all covariates will ultimately be included in the final model as PS model assumptions will also be checked via the diagnostic checklist [see section VI.B Diagnostic phase and checklist]. Missingness among covariates of interest within our study cohort will be enumerated and reported in our findings.

Table 3: Description of patient characteristics and covariate assessment windows

Covariate Category [Assessment Window]	Details	Patient Characteristics
Baseline Covariates  (Day -183 to Day -1)	Baseline (pre-admission) comorbidities, co-medications, and health resource utilization.	
 
- Lifestyle factors: History of smoking/tobacco use*, Insurance type (commercial versus Medicare/Medicaid coverage)
 
- Comorbidities and comedICATIONS: asthma, hematological cancers, solid cancers, chronic lung disease, cardiovascular disease (any), diabetes, immunosuppressive conditions, kidney or liver disease, overweight, obesity (diagnosis in medical claims/chargemaster or body mass index <math>\geq 25</math>-<math><40</math> in EHR), severe obesity (diagnosis in medical claims/chargemaster or body mass index <math>\geq 40</math> in EHR), dependence on respiratory support, frailty score, neurological/cognitive impairment, 2+ or 3+ high-risk conditions (asthma, obesity, diabetes, chronic kidney disease, severe obesity, coronary artery disease, stroke, and chronic obstructive pulmonary disease), hypertension, statin use, steroid use (any, including inhaled), any immunosuppressant use, anticoagulant and/or antiplatelet use as well as the Combined comorbidity score [Gagne 2011]
 
- Health resource utilization: Number of days hospitalized, number of outpatient visits, number of pharmacy claims, number of distinct medications dispensed, any encounter indicating skilled nursing facility, influenza vaccination status
 

Pre-admission Covariates (Day -21 to Day -1)
 
AND
 
Pre-treatment Covariates (Day 0 to Day T, inclusive)
	
COVID-19 characteristics and treatments
	
 
- Pre-treatment COVID-19 status: dyspnea or hypoxia, pneumonia, ARDS, shock, non-respiratory organ failure, other organ support procedures (ECMO, KRT, Pressors), positive SARS-CoV-2 lab test result
 
- Pre-treatment medications including those that overlap with treatment index (Day T): Anticoagulant and/or antiplatelet agents, antibiotics, other experimental COVID-19 therapy listed in NIH guidelines (hydroxychloroquine/chloroquine, remdesivir, lopinavir/ritonavir and other HIV protease inhibitors, ivermectin, IL-6 inhibitors, IL-1 inhibitors, BTK inhibitors, JAK inhibitors, interferons, convalescent plasma, IVIG-SARS-CoV-2, Mesenchymal stem cells, COVID-19 mAbs [NIH 2020(b) as of the date of protocol finalization and may be updated as deemed necessary])
 


Pre-admission Covariates (Day -21 to Day -1)
	
COVID-19 symptoms and HCRU prior to the admission date.
	
 
- COVID-19 symptoms: pre-admission COVID-19 symptoms
 
- HCRU: Inpatient hospitalization, emergency room encounter
 

Admission Covariates (Day 0; CED)
	
Demographics, hospital facility characteristics, and COVID-19 severity on the admission date.
	
 
- Hospital and admitting characteristics: Hospital setting type, hospital teaching status, hospital number of beds, admission source, emergency room encounter, ambulance encounter, admission type
 
- COVID-19 severity at admission: mWHO severity categorization on the admission date
 

Pre-treatment Covariates (Day 0 to Day T, inclusive)
	
Treatments administered prior to or concurrent with treatment index date, pre-treatment clinical status, and time from admission to treatment.
	
 
- Pre-treatment COVID-19 status: Highest recorded mWHO severity
 
- Pre-treatment utilization characteristics: Number of days hospitalized, number of days with critical/ICU care, in ICU at treatment index, number of unique department codes, number of unique procedure codes
 
- Demographics: Month of treatment index, age, sex, insurance type, US region
 

*\*Smoking/tobacco use may be under-reported [see section VIII. Limitations for additional detail]*

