**IV. DATA SOURCE**

This study uses de-identified RWD from HealthVerity comprising open and closed Medical claims and includes major payer types (commercial and federal Medicaid and Medicare programs) from all US states and territories, open and closed Medical and Outpatient Pharmacy claims, Laboratory Data including results, and Hospital Chargemaster transactional records that include diagnoses, procedures and treatments for billable inpatient and outpatient hospital encounters. The data elements derived from chargemaster data are listed in Appendix C along with their percent missingness. The database also includes clinical observations as recorded in electronic health records (EHR), where available. The open claims are sourced in near-real-time from practice management systems, billing systems and claims clearinghouses, and the closed claims are sourced from insurance providers and payers. All ages are included in the full database with ages 65 or older over-sampled to account for the under-representation of Medicare aged patients with commercial coverage. The HealthVerity Medical Claims, Pharmacy, Laboratory and Hospital Chargemaster dataset has been used for scientific publications of COVID-19 research [*Burn 2020; Gordon 2020; Harvey 2021; Murk 2020*].

As of **12-March-2021**, the data spans the time period *01-December-2018* to **22-February-2021** (the last date of available data) and included **58,233,249** patients. The data will be updated periodically as new data become available until we are able to achieve sufficient sample size, as defined in the diagnostic checklist of the statistical analysis [see *section VI.B*].

The primary endpoint of 28-day mortality is defined using Inpatient Chargemaster claims with a discharge status of ‘expired’ indicating death. Given that the HealthVerity data source is relatively new, there are no validation studies of this data source yet for mortality or other endpoints. However, use of discharge status to determine mortality endpoints among hospitalized

COVID-19 patients has been used in both in a similar chargemaster data source [*Rosenthal 2020*] and for national surveillance reporting [*CDC-NCHS 2021*].

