## B. To Be Considered in Interpretation Only

The following limitations will be taken into consideration when interpreting and disseminating the findings from the implementation of this protocol:

- **Lack of indicators of socio-economic status (SES):** The HealthVerity data leveraged for this study does not include SES. We will include insurance type in the PS model for covariate adjustment as may be indicative of SES (e.g., patients with a PPO generally have higher SES than those with HMO), but no other proxies are available to adjust for SES.
- **Lack of race/ethnicity information:** The HealthVerity data leveraged for this study does not include race or ethnicity demographic data. Therefore, we are unable to evaluate whether the effect of DEX on 28-day mortality varies by race or ethnicity, explore potential racial and ethnic disparities related to COVID-19 severity and treatment, or control for confounding by race or ethnicity.
- **Incomplete dose information:** Inpatient medication dose is not explicitly captured in the HealthVerity data. Dose can be abstracted from the free-text descriptions of the vendor codes, but requires manual review and does not allow for all medications to be assigned a dose. Thus, since a subgroup analysis by dose for DEX (or other CSIs) is not possible for all patients

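### The only socio-economic proxy, insurance type, merges Medicaid with Medicare and cannot express the plan-type contrast given as its rationale; the balance check would not see a Medicaid imbalance (minor)

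*Protocol*

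**What the plan says.** Four places in the Protocol bear on this point.

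- **Section V.F, Table 3, baseline covariates (Day -183 to Day -1).** The variable is given two levels: "Insurance type (commercial versus Medicare/Medicaid coverage". This is the only coding stated anywhere.
- **Section V.F, Table 3, pre-treatment covariates, Demographics.** Insurance type appears again, with no categories: "Month of treatment index, age, sex, insurance type, US region".
- **Section VIII.B, limitation on socio-economic status.** "The HealthVerity data leveraged for this study does not include SES". The response is: "We will include insurance type in the PS model for covariate adjustment as may be indicative of SES". The one example offered is that "patients with a PPO generally have higher SES than those with HMO", and the sentence ends "but no other proxies are available to adjust for SES". The next bullet adds that race and ethnicity are also absent.
- **Section IV.** The source is described as covering "major payer types (commercial and federal Medicaid and Medicare programs". The same section treats age 65 and over as the Medicare age range. It does not mention plan type or dual coverage.

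Three analysis rules also matter. Section VI.A fits the propensity score (PS) with main effects only. Section VI.B, Table 4, item 3 defines balance as an absolute standardized difference (ASD) of at most 0.10 and allows variables already balanced before PS matching to leave the model, with their balance rechecked afterwards. Section V.C.2, Table 2 matches age within 3 years in the risk-set sampling.

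**The concern.** One variable carries all of the SES adjustment, and its stated coding does not fit the reason given for including it. A commercial-versus-public indicator has no PPO or HMO level, so the example in Section VIII.B describes information that the Table 3 variable does not contain.

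The public level combines two programmes. Section IV ties Medicare to age. That Medicaid eligibility depends mainly on income is general knowledge and is taken here as an assumption, since the Protocol does not say so. On that assumption, the payer level most informative about SES is merged with one that largely reflects age, which the design already controls closely.

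The balance check works on covariates as coded. If the arms have the same proportion publicly insured but different Medicaid shares within it, the pooled variable looks balanced. The difference would be neither reported nor adjusted for, and some SES confounding would stay in the hazard ratio without any signal at the diagnostic phase.

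**Working it through.** The Protocol states no figure that depends on this coding, so there is nothing to reproduce. The check compares the texts and then runs an illustration on assumed inputs.

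**Text comparison**

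| Question | Section VIII.B | Table 3 coding | Section IV |
|---|---|---|---|
| Can PPO be separated from HMO? | Given as the example | No | Plan type not mentioned |
| Can Medicaid be separated from Medicare? | Not addressed | No | Both named as payer types |
| Is another SES proxy available? | No | – | – |

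**Illustration: assumed inputs, none from the Protocol**

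- Share of the cohort publicly insured, the same in both arms: 50% (30% and 70% as a range).
- Medicaid as a share of public coverage: 30% in one arm, 40-45% in the other.
- Mortality ratio (RR), Medicaid versus other coverage at the same age: 1.1-1.5.

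*Step 1. Convert to whole-cohort Medicaid prevalence.* The Medicaid shares are shares of public coverage, so they must be multiplied by the public share:

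- p0 = 0.50 × 0.30 = 0.15
- p1 = 0.50 × 0.40 = 0.20, up to 0.50 × 0.45 = 0.225

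*Step 2. Bias factor*, used as an approximation for the hazard ratio: (1 + p1(RR − 1)) / (1 + p0(RR − 1)).

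- Low end, p1 = 0.20, RR = 1.1: 1.020 / 1.015 = 1.005
- High end, p1 = 0.225, RR = 1.5: 1.1125 / 1.075 = 1.035

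The bias is about 0.5-3.5%. It pushes the hazard ratio up if the DEX+ arm has more Medicaid patients, and down by a similar amount if it has fewer. The Protocol gives no basis for choosing a direction.

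*Step 3. ASD*, using |p1 − p0| / √[(p1(1 − p1) + p0(1 − p0)) / 2].

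- Pooled variable, 50% versus 50%: 0
- Medicaid, 0.20 versus 0.15: 0.05 / √[(0.1600 + 0.1275) / 2] = 0.05 / 0.379 = 0.13
- Medicaid, 0.225 versus 0.15: 0.075 / √[(0.1744 + 0.1275) / 2] = 0.075 / 0.389 = 0.19

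*Step 4. Vary the public share.*

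| Public share | p0 | p1 | Bias factor | Medicaid ASD | Pooled ASD |
|---|---|---|---|---|---|
| 30% | 0.09 | 0.12-0.135 | 1.003-1.022 | 0.10-0.14 | 0 |
| 50% | 0.15 | 0.20-0.225 | 1.005-1.035 | 0.13-0.19 | 0 |
| 70% | 0.21 | 0.28-0.315 | 1.007-1.048 | 0.16-0.24 | 0 |

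The 0.10 in the first row is 0.098 before rounding, just inside the limit. At the 50% share, both Medicaid values fall in the 0.10-0.20 band of Table 4, item 3, where acceptance depends on the variable not predicting the outcome in the referent group. The pooled coding would never trigger that second look.

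**The case against.** The case on the other side has real weight.

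- **Age matching leaves useful signal.** With age held within 3 years, what remains in a commercial-versus-public indicator is not mainly age. Below Medicare age, on the same general knowledge used above, it is largely a Medicaid contrast. In the exploratory cohort (Appendix A.2, Table A.2), 64.8% of DEX+ and 64.3% of DEX- patients were under 70. A reader might infer that the pooled variable only duplicates age and adjusts for nothing socio-economic. The Protocol does not support that. The loss falls mainly at Medicare ages. It is somewhat wider than that because the PS has no age-by-insurance term, and because Section V.C.2 describes risk-set sampling only for the Primary Objective and Secondary Objective I.
- **PPO/HMO is only an example.** It follows an e.g. in a section on limits to interpretation, and the wording about SES is cautious. Section VIII.A separately concedes residual confounding. To say that the plan depends on the PPO/HMO contrast would be too strong. It is still the only rationale given, and the caveat does not mention the merging.
- **The coding may not be final.** Table 3 is an overview of covariates under consideration, and its second listing of insurance type has no categories. Finer levels may exist elsewhere. This stands as a caveat, but the only coding stated is the pooled one.
- **Availability is not assured.** Neither plan type nor dual coverage is shown to be in the data, and Section VIII.A says open claims lack enrollment information. This limits the fix but does not bar separating Medicare from Medicaid.
- **The 10-15 point gap is severe.** It would have to survive matching on age, sex and comorbidity and a PS containing region, utilisation and hospital characteristics. Nothing in the Protocol shows that it would. This stands in full.

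**Conclusion.** The mismatch between Table 3 and Section VIII.B is real, and so is the blind spot in the balance check. Both follow from the text. The size does not: about 0.5-3.5% on the hazard ratio, with a Medicaid ASD of about 0.13-0.19 against 0.10, rests wholly on the assumed public share, Medicaid gap and mortality ratio. Varying the public share from 30% to 70% widens the bias to about 0.3-4.8%.

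A reader might go further and conclude that the primary hazard ratio is biased by up to 6%. That would require treating Medicaid's share of public coverage as its share of the whole cohort (1.225 / 1.15 = 1.065), which is right only if every patient is publicly insured. The documents do not show that any such bias exists. Severity is minor: the coding should be clarified and split, but the point does not threaten the study's conclusions.

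**What to change.** In Section V.F, Table 3, define payer with commercial, Medicare and Medicaid as separate levels, adding dual or other if these can be identified. Use the same levels in both listings of insurance type, in the PS model and in the ASD balance table. In Section VIII.B, either add plan type to the covariate where it is recorded or delete the PPO/HMO example, and state which payer levels carry the SES adjustment.

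The cost is one to three extra PS terms. At about 12 exposed patients per covariate (Table 4, item 4), that is 12-36 DEX+ patients. The exploratory matched DEX+ versus DEX- cohort in Table A.2 had 1,840 DEX+ patients. The Protocol fixes no final sample size (Section VI.B), so the overfitting check should be rerun with the added terms. Some payer misclassification must be expected because open claims lack enrollment data. Treatment effects are not estimated during the diagnostic phase, so a recoding made in that phase would not be informed by results.

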### III. RESEARCH AIM AND OBJECTIVES

As part of the RCA with the FDA, this study informs the overall project to establish a system for rapid-cycle evaluation, using best practice scientific and operational methods, as applied to relevant and meaningful clinical questions. In this study, we seek to assess the effectiveness of DEX to reduce the risk of inpatient mortality within 28 days among US patients hospitalized with COVID-19 diagnosis or SARS-CoV-2 infection, overall and stratified by COVID-19 severity subgroups [defined according to the presence of encounters indicating supplemental oxygen or ventilation; see *section V.D* for additional subgroup detail], using the HealthVerity database.

The principles outlined by Hernan et al. emphasize the importance of explicitly emulating a hypothetical target trial when planning a RWD analysis to yield RWE [Hernan, Robins 2016; Hernan, Sauer 2016]. Although we reference the UK RECOVERY trial as a basis for comparison [RECOVERY 2020], we sought to emulate a hypothetical target trial with varied design elements, and research questions tailored for US practice and US patients. In a sensitivity analysis, we further sought to replicate the RECOVERY trial design elements (to the extent possible) [see *section VII. Sensitivity Analyses, SA8*].

Specifically, among US patients hospitalized with COVID-19 diagnosis or SARS-CoV-2 infection without prior use of any corticosteroid of interest (CSI; DEX, methylprednisolone, prednisone, hydrocortisone) estimate the hazard ratio and corresponding 95% confidence interval for the risk of inpatient mortality within 28 days after treatment initiation, comparing *new use of DEX* with:

- *non-users of corticosteroids (Primary objective I; DEX+ vs. CSI-)*, to evaluate the potential benefit of DEX above ‘standard of care’ inpatient treatment for COVID-19, where ‘standard of care’ excludes all CSIs (DEX, MPRED, PRED, HC).
- *non-users of DEX (Secondary objective I; DEX+ vs. DEX-)*, to evaluate the potential benefit of DEX above ‘standard of care’ inpatient treatment for COVID-19, where ‘standard of care’ excludes DEX but may include those newly treated with a non-DEX CSI (MPRED, PRED, HC). This comparison is most similar to the RECOVERY trial that compared DEX to ‘standard of care’ [RECOVERY 2020].

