## C. Study population

### 1. Cohort entry

#### Hospitalized Patients with COVID-19:

Patients will enter the cohort upon the admission date of the first qualifying inpatient hospitalization observed in the hospital chargemaster data. The first eligible cohort entry date is **01-April-2020**, the date when the ICD-10 code for COVID-19 diagnosis was added. The last possible cohort entry date will be 60 days prior to the last date of available data [see *Appendix A.5 Exploration 5* for additional detail justifying this design decision].

COVID-19 confirmation was defined as either of the following occurring between 21 days prior to the hospital admission date and the treatment index date, which is described in section C.2. below (inclusive; **Day -21 to Day T**):

- Outpatient medical encounter prior to or on the admission date or diagnosis 'present at admission' with ICD-10-CM diagnosis of U07.1 for COVID-19, virus identified; OR
- positive or presumptive positive SARS-CoV-2 diagnostic laboratory test result

The decision to include either diagnosis or positive laboratory test results was based on an initial exploration [see justification detail in *Appendix A.1. Exploration 1*].

For the DEX+ versus MPRED+ comparison (**Secondary Objective II**), given the increased use of MPRED earlier on in the COVID-19 pandemic, we may consider delaying the cohort entry to start in May or June pending data exploration.

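### Table 3 lists no DNR, palliative-care or comfort-care status, so neither the PS model nor the balance check can address this plausible confounder of DEX+ vs CSI-

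*Protocol*

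**What the plan says.** Section III makes the primary comparison one with "non-users of corticosteroids (Primary objective I; DEX+ vs. CSI"-, that is, with a non-active comparator. Section IV sets the outcome: "The primary endpoint of 28-day mortality is defined using Inpatient Chargemaster claims with a discharge status of" expired. Section V.E ends follow-up at death, Day T+28 or discharge.

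Table 3 in section V.F gives the candidate confounders, described as chosen a priori. Those closest to care limitation fall into two groups:

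- **Before admission (Day -183 to Day -1).** The row is described as "Baseline (pre-admission) comorbidities, co-medications, and health resource utilization". It includes "dependence on respiratory support, frailty score, neurological/cognitive impairment", "any encounter indicating skilled nursing facility" and the combined comorbidity score.
- **Up to and including Day T.** Clinical status covers "dyspnea or hypoxia, pneumonia, ARDS, shock, non-respiratory organ failure, other organ support procedures (ECMO, KRT, Pressors"). Utilization covers "number of days with critical/ICU care, in ICU at treatment index, number of unique department codes" and a count of procedure codes. Other COVID-19 therapies given up to Day T are listed, as are age and, on Day 0, admission source.

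No DNR, palliative-care, comfort-care or hospice item appears in either group. None appears in the risk-set matching criteria (Table 2), the exclusions (V.C.3), SA1 to SA8 (Table 5) or the limitations (VIII). Section VIII does name smoking, socio-economic status, race/ethnicity and dose as gaps.

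**The concern.** A patient whose care has been limited by or at the index date may plausibly be less likely to be started on a new drug and more likely to die in hospital. With a non-user comparator such patients would collect in the CSI- group. Section V.C.2 itself accepts that patients prescribed DEX may differ from those who are not.

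Three features of the plan leave the gap open.

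1. The listed severity measures largely record support received. Under section V.D a patient is classed as IMV from intubation, ventilation or ECMO procedures or an ARDS diagnosis. A patient for whom ventilation was withheld, with no ARDS coded, falls in a lower class and can be matched to someone who did not need ventilation. ICU presence at index has the same weakness.
2. Table 4 item 3 tests balance on potential confounders that have been defined. A variable that nobody defines has no standardized difference to inspect.
3. The routes that might catch it are optional. Section VI.A says automated selection (HDPS or LASSO) may be considered, and section VIII.A leaves an analysis of unmeasured confounding post hoc and only if warranted.

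At stake is a primary hazard ratio that may partly reflect who was selected for active treatment.

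**Working it through.** The protocol gives no prevalence or death risk for such patients, so there is no stated figure to reproduce. The prevalences and risk ratios below are assumptions. From the protocol come the planning HR of 0.8, 80% power with two-sided alpha 0.05, and the balance limit ASD <= 0.10 (all Table 4).

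**Bias factor.** Let pD and pC be the prevalence in DEX+ and CSI- *after* matching, and R the ratio of death risk with versus without the status, taken as equal in both arms. Approximately:

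factor = [1 + pD(R - 1)] / [1 + pC(R - 1)]

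| pD vs pC | R = 3 | R = 4 | R = 5 |
|---|---|---|---|
| 3% vs 6% | 1.06/1.12 = 0.946 | 1.09/1.18 = 0.924 | 1.12/1.24 = 0.903 |
| 4% vs 6% | 1.08/1.12 = 0.964 | 1.12/1.18 = 0.949 | 1.16/1.24 = 0.935 |

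A true HR of 1 would then read as the tabulated factor. On the log scale, 0.946 is ln(0.946)/ln(0.8) = 0.25 of the planning effect, and 0.903 is 0.46 of it.

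**Would the plan's own check see it if the variable were listed?** ASD = |pD - pC| / sqrt{[pD(1 - pD) + pC(1 - pC)]/2}.

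- 3% vs 6%: 0.03 / sqrt[(0.0291 + 0.0564)/2] = 0.03/0.2068 = 0.145. This exceeds 0.10. Table 4 can excuse an ASD of 0.10 to 0.20 only if the variable does not predict the outcome among referents, judged by an ASD below 0.10. With an assumed death risk of 30% with the status and 10% without, that ASD is 0.20/sqrt[(0.21 + 0.09)/2] = 0.52, so it would not be excused. Section VI.C would allow Cox adjustment at 0.145.
- 4% vs 6%: 0.02 / sqrt[(0.0384 + 0.0564)/2] = 0.02/0.2177 = 0.092. This would pass.

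**What remains when the check is just passed.** With pC = 5%, ASD = 0.10 corresponds to pD = 3.04%, and the factor is 0.96 (R = 3) to 0.94 (R = 5). With pC = 10% it corresponds to pD = 7.2%, and the factor is 0.95 to 0.92.

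**Chance of a false benefit.** HR 0.8 at 80% power and 1:1 allocation needs 4(1.960 + 0.842)^2 / ln(0.8)^2 = 631 events. Under no true effect, P(significant in favour of DEX) = Phi[sqrt(631/4) x |ln factor| - 1.96]. For 0.946 this is Phi(0.69 - 1.96) = 0.10, and for 0.903 Phi(1.28 - 1.96) = 0.25, against a nominal 0.025.

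**Reverse case.** With 15% in DEX+ and 10% in CSI-, the factor is 1.30/1.20 = 1.08 (R = 3) to 1.60/1.40 = 1.14 (R = 5).

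**The case against.** The strongest reply is that Table 3 is richer than its pre-admission rows suggest. Concurrent COVID-19 therapies, pressors, KRT, ECMO, ICU use, procedure and department counts and admission source run up to Day T or are taken on Day 0, and patients under comfort care would plausibly differ on many of them. This stands in part: these variables will absorb some of the imbalance, and nothing in the protocol shows that 3% vs 6% would remain after matching on them. They measure intensity of care and do not record a decision to limit it, so they do not close the gap.

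Table 3 is also presented as an overview, the components of the frailty score are not shown, and HDPS or LASSO could select such codes. All true, but none is a commitment to consider this variable.

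A reader might infer that the bias certainly favours DEX. The documents do not support that. They do not say that DEX is withheld from these patients. Because only inpatient deaths count, patients discharged alive to palliative care leave as non-events, which weakens the bias and could reverse it.

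A reader might also infer that the flag is freely available because section V.C.1 already uses a present-at-admission diagnosis, "with ICD-10-CM diagnosis of U07.1 for COVID-19, virus identified". That shows the marker in use for one code. The protocol does not show that DNR or palliative codes are filled in, and sections V.D and VIII.A say inpatient diagnoses are largely confined to admission and discharge. A sparsely coded flag could look balanced while confounding remains.

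**Conclusion.** The omission is a fact of the document. It matters because the comparator is non-use, the endpoint is inpatient death, and balance on the defined confounders governs entry to the inferential phase. It also concerns the protocol's own a priori covariate list, so it is more than a detail left to an SAP.

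The supported claim is limited: imbalance in care-limitation status that survives matching could move the primary HR, and the plan as written would not detect it. The expected direction favours DEX, on clinical reasoning that the protocol does not state. Under the illustrative inputs the HR is multiplied by 0.90 to 0.96. That is a sizeable share of the planning effect, but it rests wholly on assumed prevalences and risk ratios. It does not show that any particular result would be false.

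How to treat hospice discharges as outcomes is a question of informative censoring and separate from this point.

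**What to change.** 1. Add to Table 3 a flag for any DNR or palliative-care record dated Day -183 to Day T or marked present at admission. Never build it from discharge-only codes, which may reflect events after index.
2. Include the flag among the candidate PS covariates and in the Table 4 item 3 balance list.
3. Report its capture in each arm, so that readers can judge whether apparent balance means anything.
4. Rerun the primary HR excluding flagged patients.
5. Name incomplete capture of care-limitation status as a limitation in section VIII.

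The cost is one covariate definition and one rerun. Under the plan no treatment effect is estimated before the inferential phase, so adding the flag before then keeps it a priori. The downside is that coding is incomplete, so adjustment will be partial.
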